Timing of Assessments: Initial evaluations will be performed \leq 14 days before starting natural progesterone. Subsequent evaluations will be at the following time points after initiation of study therapy (4 weeks \pm 3 days, 8 weeks \pm 1 week, 24 weeks \pm 2 weeks) with one final off-study evaluation if it is prior to the 24 week evaluation and $>$ 2 weeks from previous evaluation (this evaluation would be the visit when patient comes off study).

QOL Questionnaires: EORTC Quality of Life Questionnaire-Core 30/Brain Cancer Module-20 (EORTCQLQ30/BN20); M. D. Anderson Symptom Inventory Brain Tumor Module (MDASI-BT)

2. Objectives (and Endpoints)

Our main goal is to establish pharmacokinetics, safety/tolerability and efficacy of daily subcutaneous natural progesterone for the treatment of patients with recurrent glioblastoma. The specific objectives/endpoints of this study are listed below.

OBJECTIVES	ENDPOINTS
Primary	

Protocol Title: Pilot study of progesterone for recurrent GBM

OBJECTIVES	ENDPOINTS

To determine that the pharmacokinetics of natural progesterone given to recurrent GBM patients by subcutaneous injection is consistent with previous determinations made using the aqueous formulation of progesterone (IBSA Institut Biochimique SA, Lugano, Switzerland) given subcutaneously.To determine the safety of administering daily subcutaneous natural progesterone for the treatment of patients with recurrent GBMs.To determine the ORR [defined as stable disease (SD) or better (PR or CR)] at 8 weeks in eligible patients with recurrent GBM treated with daily subcutaneous natural progesterone.	
Pharmacokinetic: Plasma progesterone levels at 0, 30 min, 1, 2, 4, 6, 8 hrs from 1st injection and at 8 prior to drug injection in 3 pts at each dose level. (May alternatively be done on any day after the 1st week during the initial 4 weeks with no need for day 8 trough draw if done later)Safety: Adverse events, clinical assessments (eg. vital sign, physical, etc.), clinical laboratory test.Efficacy: Overall response rate (ORR) per protocol volumetric definition at 8 weeks from initiation of progesterone.
Secondary	

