5.7 Description of Study Procedures

Medical history

Findings from medical history (obtained at screening) and physical examination shall be given a baseline grade according to the procedure for AEs. Increases in severity of pre-existing conditions during the study will be considered AEs, with resolution occurring when the grade returns to the pre-study grade or below.

Physical examination

Physical examinations should be conducted according to the Schedules of Assessments. Full physical examinations should be conducted at screening/baseline and the EOS visit (evaluate all major organ systems, including the following categories: general, head, eyes, ears, mouth/throat, neck, heart, lungs, abdomen, lymph nodes, joints, extremities, integumentary, neurologic, and psychiatric). Other examinations may be focused, at the discretion of the Investigator, to identify changes from baseline or evaluate changes based on the patient's clinical symptoms. Weight is to be recorded at each visit, height at screening/baseline visit only.

Neurological assessment

Will be assessed with timing according to the Schedules of Assessments. Although not used for determining response, it is useful to evaluate improvement in the neurologic exam, as compared with the baseline assessment, that should coincide with objective measurement of tumor size.

NEURO EXAM STATUS (compared to pre-treatment exam)	
Better	Must be on stable or decreasing dose of steroids
Same	Failure to qualify for better or worse
Worse	Include patients requiring increasing steroid doses to remain stable

Performance status assessment

Patients will be graded with timing according to the Schedules of Assessments on the Karnofsky Performance Scale (**Appendix 1**).

Vital signs

Vital signs (blood pressure [BP], pulse, temperature, and respiration rate) will be evaluated according to the Schedules of Assessments. Body weight is also recorded along with vital signs.

Clinical laboratory tests

The following clinical laboratory tests will be performed (see Schedules of Assessments):

- CBC with differential
 - Includes hemoglobin/hematocrit, white blood cells with automated differential, platelets
- Complete metabolic panel (CMP)
 - Includes sodium, potassium, bicarbonate, chloride, BUN, creatinine, calcium, glucose, total bilirubin, SGOT (AST), SGPT (ALT), alkaline phosphatase, albumin, total protein
- Pregnancy test (female subjects of childbearing potential (FCBP) only)
 - Criteria for those not considered FCBP

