 - Age \geq 55 years and one year or more of amenorrhea
 - Age $<$ 55 years and one year or more of amenorrhea, with estradiol $<$ 20 pg/ml
 - Age $<$ 55 with prior hysterectomy but intact ovaries, with estradiol $<$ 20 pg/ml
 - Prior bilateral oophorectomy

Toxicity (Adverse Event) assessment

Toxicities will be scored according to CTCAE v5.0. Evaluations for toxicity will be performed weekly during the 1st 4 weeks of progesterone therapy followed by every 4 weeks thereafter (through a total of up to 24 weeks drug therapy). Final assessment (EOS visit) will be 4 weeks after last drug dose.

MRI brain with and without contrast

Diagnostic brain MRI scans with and without contrast will be utilized to assess for response with timing according to the Schedules of Assessments. DSC perfusion imaging will also be obtained, if possible, but is not required. Volumetric assessment of progressive measurable contrast-enhancing disease ($\geq 1 \text{ cm}^3$) will be performed at baseline. If there is no measurable disease at trial baseline scan (e.g. gross resection of all recurrent enhancing disease), patient is still eligible for study but will be assessed for progression based on criteria for non-evaluable disease ($< 1 \text{ cm}^3$ of recurrent enhancing disease).

Imaging response criteria is defined below:

Measurable Disease: Measurable lesions are those with clearly defined margins by contrast-enhanced MRI scan that is at least 1 cm^3 in volume. All measurable lesions will be considered together. Clear enhancing lesions representing progressive tumor pre-treatment that is less than 1 cm^3 in volume will be considered non-evaluable disease.

Objective Status, To Be Recorded at Each Evaluation: Unless progression is observed, objective status can only be determined when ALL measurable sites and lesions are assessed.

Response Definitions:

- **Complete Response (CR):** Complete disappearance of all measurable disease in contrast-enhancing MRI. No new lesions. No evidence of non-evaluable disease. All measurable lesions and sites must be assessed using the same techniques as baseline. Patients must be on no steroids. If there is no enhancing disease present at baseline, then this criteria will not apply and the case will not be considered in the N when evaluating for % of patient achieving CR.

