- **Partial Response (PR):** (Measurable disease only) Greater than or equal to 65% decrease under baseline in total tumor volume of all measurable lesions. No progression of non-evaluable disease (defined as progression to at least 1.5 cm^3 in volume). No new lesions. All measurable lesions and sites must be assessed using the same techniques as baseline. If there is only non-evaluable disease or no enhancing disease present at baseline, then this criteria will not apply and the case will not be considered in the N when evaluating for % of patient achieving PR.
- **Stable Disease (SD):** Does not qualify for CR, PR, or progression. The designation of SD requires a minimum of 8 weeks duration (2 assessment of stable disease from baseline at least 4 weeks apart). All measurable sites must be assessed using the same techniques as baseline. The steroid dose at the time of the scan evaluation should be no greater than the maximum dose used in the first 8 weeks from initiation of therapy.
- **Progressive Disease (PD):** 40% increase in the tumor volume of all measurable lesions over previous exam (over baseline if no decrease) using the same techniques as baseline, OR clear progression of non-evaluable disease (defined as growth to at least 1.5 cm^3 in volume), OR clear appearance of any new measurable lesion/site, OR clear clinical worsening or failure to return for evaluation due to death or deteriorating condition (unless clearly unrelated to this cancer).

Best Response: This will be calculated from the sequence of objective statuses. For patients with all disease sites assessed every evaluation period, the best response will be defined as the best objective status as measured according to the above criteria.

Pharmacokinetic Testing (Research)

Protocol Title: Pilot study of progesterone for recurrent GBM

Number of patients tested: The first three patients of a treatment dose level will be undergo pharmacokinetic testing for plasma level of progesterone.

Timing of Assessments: Pharmacokinetic samples will be obtained on day 1 of therapy. Plasma samples will

be obtained immediately prior to administration of drug and, subsequently, at 30 minutes, 1 hour, 2 hour, 4 hours, 6 hours, and 8 hours after drug injection. Additional sample will be obtained prior to the day 8 injection. (May alternatively be done on any day after the 1st week during the initial 4 weeks with no need for day 8 trough draw if done later)

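### The steroid condition for stable disease is met automatically at any scan by day 56, so a patient held stable on rising steroids can count as an 8-week response

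*Combined protocol and SAP*

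**What the plan says.** The third primary objective in Section 2 is "To determine the ORR [defined as stable disease (SD) or better (PR or CR)] at 8 weeks in eligible patients with recurrent GBM", and the matching endpoint is "Overall response rate (ORR) per protocol volumetric definition at 8 weeks from initiation of progesterone". SD is therefore a success, and the clock starts at the first progesterone dose.

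The response definitions in Section 5.7 treat steroids differently by category:

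- **CR:** "Patients must be on no steroids".
- **PR:** "Greater than or equal to 65% decrease under baseline in total tumor volume of all measurable lesions", with further conditions on new lesions and non-evaluable disease, but none on steroids.
- **SD:** the residual category, needing two assessments at least 4 weeks apart, with the condition "The steroid dose at the time of the scan evaluation should be no greater than the maximum dose used in the first 8 weeks" measured from initiation of therapy.
- **PD:** imaging limbs, then "OR clear clinical worsening or failure to return for evaluation due to death or deteriorating condition", unless clearly unrelated to the cancer. A steroid increase is not named.

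The neurological table in the same section rates as *Worse* a patient described by "Include patients requiring increasing steroid doses to remain stable". The text above that table says the assessment does not determine response.

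The ORR count also drives the single futility look (Sections 5.2 and 15.1): 2 or more responders among the first 10 continues, 1 or fewer stops. Those sections put the response rate under ineffective therapy at 10%.

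**The concern.** A steroid condition on SD is there to stop a scan from being called stable when the steroid dose has gone up to keep it so. The protocol clearly regards steroids as relevant: CR forbids them, SD has a clause about them, and the neurological rating of *Better* requires a stable or falling dose. But the SD clause compares the dose at the scan with a maximum taken over a period that normally contains that scan. At the primary time point it then has nothing to test.

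SD is what the primary analysis mainly looks for. Section 15.1 expects patients with an enhancing recurrence to keep progressing unless the therapy works. That inference weakens if a rising steroid dose, rather than progesterone, can account for a stable scan. There is no concurrent control to absorb such an error, and with a boundary at 2 of 10 a single misclassified patient can turn a stop into a continue.

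**Working it through.** The plan gives no power, alpha or target rate for this endpoint (Section 15.1 says the 20 patients need no further justification), so there is no figure to reproduce. The check is logical first, then arithmetical.

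**Step 1. Does the condition have content at 8 weeks?** Let D(t) be the steroid dose on day t of therapy. The SD clause requires D(scan) ≤ max{D(t): t within the first 8 weeks}. If the scan is on or before day 56, D(scan) is a member of that set and the inequality always holds. The 4-week scan, the other one needed for SD, always lies inside the period.

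**Step 2. When can it fail?** The Section 1.3 footnote allows the 8-week MRI ± 1 week (days 49–63). Section 5.6 allows ± 2 weeks for scans after the 4-week MRI (days 42–70). Failure needs a scan after day 56 and a dose above every dose of the first 8 weeks. If the visit numbering d1, d29 is continued to d57, a scan on the nominal day sits just outside the reference period, but it still fails only if that day's dose is a new peak.

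Listing every weekly dose path with three dose levels gives:

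| Scan week | Paths | Fail as written | Fail against pre-treatment dose |
|---|---|---|---|
| 6 | 2,187 | 0 | 33.3% |
| 7 | 6,561 | 0 | 33.3% |
| 8 | 19,683 | 0 | 33.3% |
| 9 | 59,049 | 513 (0.87%) | 33.3% |
| 10 | 177,147 | 1,539 (0.87%) | 33.3% |

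At week 9 the failures are 1 path (all earlier doses at the lowest level, then the middle level) plus 2^9 = 512 paths (all earlier doses below the top level, then the top level). Paths are weighted equally. The table shows what the rule can detect and is not an estimate of clinical frequency.

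**Step 3. Does another rule close the gap?** CR does, for CR only. PR has no steroid condition. The neurological *Worse* rating describes exactly this patient but is kept out of response. The clinical limb of PD reaches a patient who clearly worsens, but it does not clearly reach one whom more steroid keeps stable.

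**Step 4. What could it do to the futility rule?** Inputs: p0 = 0.10 and the boundary of 2 in 10, both from Section 15.1. Assumption: a share m of true progressors is masked and called SD or PR. The documents give no value for m, so the range 0–30% is used.

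Apparent rate p = 0.10 + 0.90 × m

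P(continue) = 1 − (1 − p)^10 − 10 p (1 − p)^9

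| m | p | P(continue) | Expected responders in 20 |
|---|---|---|---|
| 0% | 0.100 | 1 − 0.349 − 0.387 = 0.264 | 2.0 |
| 5% | 0.145 | 0.437 | 2.9 |
| 10% | 0.190 | 1 − 0.122 − 0.285 = 0.593 | 3.8 |
| 20% | 0.280 | 0.817 | 5.6 |
| 30% | 0.370 | 0.932 | 7.4 |

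For the final report, two extra misclassified patients would move the exact 95% interval from 1.2%–31.7% (2 of 20) to 5.7%–43.7% (4 of 20).

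**The case against.** A reader might infer that the condition can never fail at the 8-week assessment and that every steroid-masked progression is scored as a response. The documents do not support either statement. Late-window scans can fail, and the nominal scan may itself fall on d57. The clause can also do its job at the later scans, when the dose is compared with a period that has closed. A patient whose steroids are raised because of evident decline may already be PD through the clinical limb, and CR is fully protected. The exposed case is narrower: a patient whose dose rose by day 56, who stayed clinically stable, and who is classed as SD or PR.

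A reader might also take the probabilities above as an estimate of bias. They are not. The documents do not give the masked share. Nor does Section 15.1 say how the 10% rate was defined: if it already includes patients held stable on steroids, adding m on top counts them twice.

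Finally, this is a Phase 1 pilot. The expansion gives a preliminary efficacy assessment, ORR is reported with an interval and not tested, and the only formal decision affected is whether to continue to 20 patients.

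All of this stands, and it limits the scope and size of the point. It does not restore the clause: no other rule gives it content for a scan by day 56, and none adds a steroid condition to PR.

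**Conclusion.** The point holds in a bounded form. For any scan on or before day 56 the SD steroid condition is true by definition, and PR has none. A patient kept clinically stable by rising steroids in weeks 1–8, and not meeting the clinical limb of PD, can therefore be counted as a success in the 8-week ORR and in the futility count. Any such misclassification favours the drug.

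The logical part rests only on the protocol's text. The size is unknown: an ineffective drug's chance of passing futility runs from 0.26 with no masking to 0.93 if 30% of progressors are masked, assuming the 10% background rate excludes masked patients. The rule should be corrected before responses are counted, because it guards the primary endpoint and as written does almost nothing there.

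**What to change.** In Sections 5.7 and 15.1, with the futility text in Section 5.2 brought into line, add a rule that applies **only to the 8-week ORR and the interim futility count**:

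- Count SD or PR as a response only if the steroid dose at the scan is no greater than the last dose recorded before the first progesterone injection (screening or d1).
- Count a patient who fails this as a non-responder for those two counts, without relabelling the patient as PD.
- Exempt a steroid increase documented as clearly unrelated to the tumour, parallel to the exception in the PD definition.
- Report ORR under the current definition as a sensitivity analysis.

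This is a counting rule and not a rule about steroid use. The SD wording should otherwise stay as it is, because Sections 5.1 and 8.1 use SD or better at 24 weeks when continued drug is considered, and a global change would reach that decision. Separately, the sponsor should reconcile the SD, PR and PD definitions with the neurological table, and the two MRI windows in Sections 1.3 and 5.6 with each other.

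The cost is a few sentences. Section 1.3 already schedules steroid documentation at screening, d1, d8, d15, d22, d29 and every 4 weeks, and the current clause already needs the dose at the scan. The downside is that the reported ORR may be lower and futility somewhat more likely to be declared.

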8.1 Duration of therapy

In the absence of treatment delays due to adverse event(s), patients will be treated up to 24 weeks until any one of the following:

- Tumor progression per protocol-specified criteria
- Death
- Unacceptable toxicity
- Symptomatic deterioration
- Investigator's decision to discontinue treatment
- Patient decision to discontinue treatment
- Patient withdraws consent
- Lost to follow up

In the event of a patient's withdrawal, the Investigator will make every effort to complete the End of Treatment procedures specified in the Schedule of Events.

Patients who are tolerating the drug with stable disease (SD) or better after 24 weeks of therapy may be considered for compassionate use continuation on a case-by-case basis after discussions between the patient, treating physician and the study supporter (IBSA Institut Biochimique SA, Lugano, Switzerland). It is at the discretion of the Investigator to continue treating patients in this circumstance as long as IBSA agrees to continue to provide drug until unacceptable toxicity, withdrawal by patient and/or treating physician or disease progression. Followup evaluations under these circumstances will be considered standard-of-care at the discretion of the patient's treating physician.

8.2 Duration of follow-up

Patients will be followed for approximately 4 weeks (to up to 6 weeks) after the last dose of study drug at which point they will have their end-of-study (EOS) visit. Patients removed from study for unacceptable adverse event(s) will be followed until resolution or stabilization of the adverse event.

While patients will not undergo official visits for long-term follow-up after their EOS visit, further data for PFS and OS endpoints may be obtained based on chart review of standard-of-care visits with the subject's treating physician(s) unless the patient specifically request not to be followed in such fashion after coming off study.

Patient records may be reviewed until death to assess progression and survival. Survival information may be collected by clinic visit, email, or telephone after ending protocol treatment and until the study is terminated, the patient dies, or the patient is lost to follow-up.

Protocol Title: Pilot study of progesterone for recurrent GBM

A participant will be considered lost to follow-up if he fails to return for three scheduled visits and is unable to be contacted by the study site staff after three attempts at contact by phone.

The following actions must be taken if a participant fails to return to the clinic for a required study visit:

The site will attempt to contact the participant and reschedule the missed visit and counsel the participant on the importance of maintaining the assigned visit schedule and ascertain if the participant wishes to and/or should continue in the study.

Patients removed from study for unacceptable adverse event(s) will be followed until resolution or stabilization of the adverse event.

In case of a clinically significant AE, patient will be followed for safety until resolution or permanent sequelae of all toxicities attributable to study drug(s). If the patient discontinues study drug for a clinically significant AE, the patient will be followed until resolution of the AE or the event is considered to be stable and/or chronic.

9. Inclusion and Exclusion Criteria

Minorities and Women: Subjects will be approximately representative of the demographics of the patient population at Emory University. This study is designed to include women and minorities, but is not designed to measure specific sex differences of intervention effects. While males and females will be recruited with no preference to gender, and based on the results of previous studies, we expect 50% of our accrual to be female. No exclusion to this study will be based on race or sex. Minorities will actively be recruited to participate. However, based on previous enrollment, we expect about 35% of subjects to be minorities.

Accrual Targets					
Ethnic Category	Sex/Gender				
	Females		Males		Total
Hispanic or Latino	2	+	2	=	4
Not Hispanic or Latino	11	+	11	=	22
Ethnic Category: Total of all subjects	13	+	13	=	26
Racial Category					
American Indian or Alaskan Native	0	+	0	=	0
Asian	1	+	1	=	2
Black or African American	2	+	2	=	4
Native Hawaiian or other Pacific Islander	0	+	0	=	0
White	10	+	10	=	20
Racial Category: Total of all subjects	13	+	13	=	26

	(A1 = A2)	(B1 = B2)	(C1 = C2)
Accrual	Total Expected		
Rate: 1-2 pts/month	Accrual: 20 Min	26 Max	
Projected Start			
Date of Study: April 1, 2021			

Inclusion Criteria

- Patients must have pathologic confirmation of a glioblastoma or gliosarcoma diagnosis at initial surgery or second or later surgery.
- Patients may have had up to two previous salvage agents administered for treatment of recurrent GBM (may be at 1st, 2nd or 3rd recurrence).
- Patients must be ≥ 18 years of age.
- Patients must be able to have MRI scans for disease follow up.
- Recurrent GBM must consist of a minimum of 1 cm³ of contrast enhancing disease on high resolution T1 post-contrast sequence as defined on pre-treatment MRI obtained within 14 days of initiating therapy. In the setting of recurrent GBM that was managed with surgery, there is no minimum disease required and the criteria for non-measurable/evaluable disease will be applied to determine imaging response (see Section 5.7).
- Patient must have the following lab values ≤ 14 days prior to registration:
 - WBC $\geq 3,000/\mu\text{L}$
 - ANC $\geq 1,500/\mu\text{L}$
 - platelet count of $\geq 75,000/\mu\text{L}$ (transfusion is not allowed within 1 week of a qualifying minimum platelet level to achieve eligibility)
 - hemoglobin ≥ 9.0 gm/dL (transfusion is allowed to reach minimum level)
 - AST/ALT $\leq 2.0\times$ UNL
 - bilirubin $\leq 2 \times$ UNL
 - creatinine ≤ 1.5 mg/dL
- Patients must have a life expectancy of ≥ 12 weeks.
- Patients must have a Karnofsky Performance Status (KPS) ≥ 60 .
- Patients who are women of childbearing potential must have a negative pregnancy test documented ≤ 14 days prior to registration and agree to use adequate barrier contraceptive methods or abstinence for duration of study.
- Patients who are men must agree to not father a child while on study and agree to use adequate barrier contraceptive methods or abstinence for duration of study.
- Patients must be able to understand and provide written informed consent.
- Both men and women, and members of all races and ethnic groups are eligible for this trial. Subjects will be approximately representative of the demographics of the referral base for the participating institutions.
- Patient must not have a known allergy to progesterone.
- In females, no active vaginal bleeding.
- Patients may not be enrolled on any other therapeutic trial for which they are receiving an anti-tumor therapy.

Exclusion Criteria

- Patients with pacemakers, aneurysm clips, neurostimulators, cochlear implants, metal in ocular structures, history of being a steel worker, or other incompatible implants which makes MRI safety an issue are excluded.

- Patients that have any significant medical illnesses that in the investigator's opinion cannot be adequately controlled with appropriate therapy or would compromise the patient's ability to tolerate this therapy are excluded.
- Patients with uncontrolled hypertension
- Patients with a history of severe hepatic dysfunction of disease, liver tumors or any active liver disease are excluded.
- Patients with a history of idiopathic jaundice, severe pruritis and pemphigoid gestastationis during pregnancy are excluded.
- Patients with a history of breast or genital tract cancer are excluded.
- Patients with a history of any other invasive cancer (except non-melanoma skin cancer and excluding carcinoma in-situ), unless in complete remission and off all therapy for that disease for ≥ 3 years, are ineligible.
- Patients with an active infection or serious intercurrent medical illness are ineligible.
- Patients who have received any radiation therapy within 4 weeks (for recurrent GBM) or 90 days (for initial diagnosis of GBM) of the start of progesterone therapy are ineligible.
- Patients who received any other in anti-tumor agents (including investigational anti tumor agents, but excluding avastin) must be off therapy for 4 weeks prior to initiating progesterone on study. Patients on avastin at enrollment will be allowed to be maintained on their current dose of avastin when they begin progesterone. Patients receiving anti-coagulation therapy are excluded.
- Patients that underwent resection for their recurrent GBM need to wait at least 4 weeks before they can initiate progesterone treatment.
- Patients with active or recent (within 6 months) thromboembolic disease are excluded.
- Patients with current ongoing therapy with estrogen/progesterone (including hormonal contraceptives) are excluded. Would need to stop this form of birth control at least 7 days prior to initiation of therapy to be eligible.

10. Local Number of Participants

We will be recruiting all participants (up to 32 patients) at the Winship Cancer Institute of Emory University. Patients will be registered after signing of the informed consent document and meeting all entry requirements.

11. Recruitment Methods

Subjects will be recruited from recurrent GBM patients referred by neurosurgery, neuro-oncology or radiation oncology. Initial screening will be conducted/reviewed by clinical investigators and/or their trained designee (e.g. research nurse, research coordinator, etc.). Cases will be identified from the neurosurgery/neuro-oncology/radiation oncology outpatient clinics or neurosurgery/oncology inpatient services. After potential subjects have been identified, their clinical care team at Winship will inform potential subjects about the known benefits and potential risks of a clinical trial as well as other available treatment options.

Protocol Title: Pilot study of progesterone for recurrent GBM

Some of the subjects recruited for this protocol will be patients being treated at Emory and under the care of one or more of the study investigators. Some potential subjects will be identified by their treating physician and referred to Emory for possible participation in the protocol.

No incentives are provided to patients for trial participation.

Study personnel will notify Winship Central Subject Registration (WCSR) by email at [contact], once subject has been consented for a trial.

Email notification must be done within 24 hours after consent has been obtained and it will include scanned copies of:

- Signed patient consent form (which includes a HIPAA authorization component)
- Emory Research Management System (ERMS; <https://erms.emory.edu>) Enrollment Fax Cover

The WCSR will enter the subject into the OnCore Research Management System, which is the system of record for Winship Cancer Institute Clinical Trials.

Enrolling a subject requires careful screening and determination of eligibility.

Eligible patients will be enrolled on study centrally at Winship Cancer Institute by the Study Coordinator.

When all required test results are available, complete the eligibility checklist and provide the checklist and the supporting documentation to the IRB-approved investigator for review and sign-off. This eligibility checklist is to be verified by 2 people (the investigator and CRN/CRC). Once the investigator (sub-investigator, Co-Investigator) has signed the eligibility checklist, enrollment may proceed. OnCore and ERMS must be updated to reflect eligibility and on treatment status.

Following enrollment, patients should begin protocol treatment within 5 business days. Issues that would cause treatment delays should be discussed with the Principal Investigator.

12. Withdrawal of Participants

Participants are free to withdraw from participation in the study at any time upon request.

An investigator may discontinue or withdraw a participant from the study for the following reasons:

- Pregnancy
- Significant study intervention non-compliance
- If any clinical adverse event (AE), laboratory abnormality, or other medical condition or situation occurs such that continued participation in the study would not be in the best interest of the participant
- Any specific contraindication for use of progesterone (e.g. thromboembolic event)
- Disease progression which requires discontinuation of the study intervention
- If the participant meets an exclusion criterion (either newly developed or not previously recognized) that precludes further study participation
- If the treating physician feels that doing so would be in the best interest of the patient
- Participant unable to receive progesterone for > 14 days

The reason for participant discontinuation or withdrawal from the study will be recorded on the study Case Report Form (CRF). Subjects who sign the informed consent form but do not receive the study intervention may be replaced. Subjects who sign the informed consent form and receive the study intervention, and subsequently withdraw, or are withdrawn or discontinued from the study, will be replaced only if they receive less than 28 days of progesterone.

13. Risks to Participants

Risks associated with additional blood draws. There are some additional blood draw for research purposes (e.g. PK evaluations, when required, and serum biomarkers) that may be required. The physical risk of drawing blood is local pain and bruising at the site of venipuncture. Qualified phlebotomists or designee will draw blood samples. Care will be taken to obtain these specimens in a safe and hygienic manner. A small number of people experience lightheadedness or fainting. There is a slight risk of infection. To minimize these risks, attempts will be made to draw study blood samples at the same time as blood draws needed for routine clinical care are obtained. Repeated blood drawing may be associated with iron deficiency anemia.

Data security- Subjects will be asked to provide personal health information (PHI). All attempts will be made to keep this PHI confidential within the limits of the law. However, there is a chance that unauthorized persons will see the subjects' PHI. All records will be kept in a locked file cabinet or maintained in a locked room at the participating sites. Electronic files will be password protected behind an academic institutional firewall. Only people who are involved in the conduct, oversight, monitoring, or auditing of this study will be allowed access to the PHI that is collected. Any publications from this study will not use information that will identify subjects. Organizations that may inspect and/or copy research records maintained at the participating sites for quality assurance and data analysis include groups such as the National Cancer Institute (NCI) and Food and Drug Administration (FDA).

Risks associated with daily subcutaneous drug injections. There are potential risks from the daily injection of drug including injection site reactions (irritation, pain, pruritis, and swelling). Infection can also potentially develop. Potential effects of the drug is documented below.

Risks associated with administration of natural progesterone. Potential effects of the drug are documented below. The list shows what has been previously established for subcutaneous progesterone; which is an aqueous formulation currently available in Europe.

As per the manufacturer of subcutaneous progesterone (IBSA Institut Biochimique SA), repeated doses of progesterone may have the following side effects:

Undesirable effects: The most frequently reported adverse drug reactions during treatment with subcutaneous progesterone during clinical trial are administration site reactions, breast and vulvo-vaginal disorders. The table below displays the main adverse drug reactions in women treated with subcutaneous progesterone in the pivotal clinical trial. Data are expressed by system organ class (SOC) and frequency.

Overdose: High doses of progesterone may cause drowsiness. Treatment of overdose consists of discontinuation of subcutaneous progesterone together with initiation of appropriate symptomatic and supportive care.

System Organ Class (SOC)	Very common (≥ 1/10)	Common (≥ 1/100 to < 1/10)	Uncommon (≥ 1/1000 to < 1/100)
Psychiatric disorders			Mood altered
Nervous system disorders		Headache	Dizziness Somnolence

Gastrointestinal disorders		Abdominal distension Abdominal pain Nausea Vomiting Constipation	Gastrointestinal disturbances
Skin and subcutaneous tissue disorders			Pruritus Rash
Reproductive system and breast disorders	Uterine spasm Vaginal haemorrhage	Breast tenderness Breast pain Vaginal discharge Vulvo-vaginal pruritus Vulvo-vaginal discomfort Vulvo-vaginal infl OHSS	Breast disorders
General disorders and administration site conditions	Administration site reactions*	Injection site haematoma Injection site induration Fatigue	Feeling hot Malaise Pain

*Administration site reactions, such as irritation, pain, pruritus and swelling.

(Reference: <https://www.assistingnature.gr/wp-content/uploads/2017/07/Prolutex.pdf>)

14. Potential Benefits to Participants

While pre-clinical evidence suggests possible anti-GBM activity for progesterone and one of the primary objectives of this study is to measure objective response at the 8 week MRI, there is no guarantee of benefit to subjects who enroll in this protocol.

15. Data Management and Confidentiality

